6.1.6 Renal adverse events

Elevated creatinine and biopsy confirmed tubulointerstitial nephritis and allergic nephritis have been infrequently observed following treatment with nivolumab. Most cases were Grade 2 or Grade 3 and based on creatinine elevation. Events were managed with corticosteroids and in all cases renal function partially or fully improved. As creatinine abnormalities are common in patients with CLL and other comorbidities, it is important that an evaluation/work-up distinguish between non-drug-related causes (eg, dehydration, concomitant medications, hypotension, progression of disease) and a possible drug-related AE as the management is quite different. The principal treatment for renal AEs is corticosteroids.

Grade of Creatinine Elevation	Management	Follow-up
Grade 1 (Creatinine > ULN and > than baseline but \leq 1.5x baseline)	
 Continue nivolumab Monitor creatinine weekly 	
If returns to baseline:
 
 Resume routine creatinine monitoring per protocol 
If worsens:
 
 Treat as Grade 2 or 3-4
Grade 2-3 (Creatinine > 1.5x baseline to \leq 6x ULN)	
 Delay nivolumab Monitor creatinine every 2-3 days Steroids: 0.5-1 mg/kg/day methylprednisolone IV or oral equivalent Consider renal biopsy 	
If returns to Grade 1:
 
 Taper steroids over at least 1 month, consider prophylactic antibiotics for opportunistic infections, and resume nivolumab and routine creatinine monitoring per protocol

		If elevations persist >7 days or worsen: 
 ▪ Treat as Grade 4
Grade 4 (Creatinine > 6x ULN)	
 ▪ Discontinue Nivolumab ▪ Monitor creatinine daily ▪ Steroids: 1-2 mg/kg/day methylprednisolone IV or IV equivalent ▪ Consult nephrologist ▪ Consider renal biopsy 	If returns to Grade 1: 
 ▪ Taper steroids over at least 1 month add prophylactic antibiotics for opportunistic infections

Patients on IV steroids may be switched to an equivalent dose of oral corticosteroids (e.g. prednisone) at start of tapering or earlier, once sustained clinical improvement is observed.

6.1.7 Neurologic adverse events

Neurologic AEs have been uncommonly observed following treatment with nivolumab. Neurologic AEs can manifest as central abnormalities (eg, aseptic meningitis, encephalitis) or peripheral sensory/motor neuropathies (eg, Guillain-Barre Syndrome). Early recognition and treatment of neurologic AEs is critical to its management. Patients should be advised to seek medical evaluation if they notice impairment in motor function (eg, weakness), changes in sensation (eg, numbness), or symptoms suggestive of possible central nervous system abnormalities such as new headache or mental status changes. As neurologic symptoms can be common in patients with cancer, it is important that an evaluation/work-up distinguish between non-drug-related causes (eg, progression of disease, concomitant medications, infection) and a possible drug-related AE as the management is quite different.

Grade of Neurological Toxicity	Management	Follow-up
Grade 1 (Asymptomatic or mild symptoms; intervention not indicated)	
 ▪ Continue nivolumab 	
 ▪ Continue to monitor patient If worsens: 
 ▪ Treat as Grade 2 or 3-4
Grade 2 (Moderate symptoms; limiting instrumental ADL)	
 ▪ Delay nivolumab ▪ Symptomatic treatment ▪ Steroids: 0.5-1 mg/kg/day methylprednisolone IV or oral equivalent 	If improves to baseline: 
 ▪ Resume nivolumab If worsens: 
 ▪ Treat as Grade 3-4
Grade 3-4 (Severe symptoms; limiting self-care ADL; life-threatening)	
 ▪ Discontinue Nivolumab ▪ Neurology consult ▪ Symptomatic treatment ▪ Steroids: 1-2 mg/kg/day methylprednisolone IV or IV equivalent ▪ Add prophylactic antibiotics for opportunistic infections 	If improves to Grade 2: 
 ▪ Taper steroids over at least 1 month If worsens or atypical presentation: 
 ▪ Consider IVIG or other immunosuppressive therapies

Patients on IV steroids may be switched to an equivalent dose of oral corticosteroids (e.g. prednisone) at start of tapering or earlier, once sustained clinical improvement is observed.

6.1.8 Lipase/Amylase Elevations

Asymptomatic elevations in lipase and amylase have been reported. In monotherapy studies of nivolumab, lipase and amylase levels were not systematically monitored, so an estimate of the frequency of asymptomatic lipase/amylase elevations is unknown. In a study evaluating the safety of the nivolumab + ipilimumab combination in melanoma, lipase and amylase levels were systematically monitored and the frequency of any grade lipase/amylase AEs was 29% and Grade 3-4 were 18%. Very few patients reported associated symptoms (eg, abdominal pain) or radiographic findings (eg, stranding) consistent with pancreatitis. Thus, there does not seem to be clinical significance to the elevated laboratory values. As lipase/amylase abnormalities are not uncommon in patients with cancer, it is important that an evaluation/work-up distinguish between non-drug-related causes (eg, progression of disease, concomitant medications, alcohol) and a possible drug-related cause as the management is quite different. The recommended management of nivolumab-related elevated lipase/amylase values centers around close observation. Physicians should ensure patients have no associated symptoms consistent with pancreatitis such as abdominal pain. Corticosteroids do not seem to alter the natural history of lipase/amylase elevations. Laboratory values tend to fluctuate day to day and eventually return to baseline or low grade over the course of weeks whether or not patients receive corticosteroids. Asymptomatic elevations should be monitored approximately weekly. For patients with elevated lipase/amylase and symptoms consistent with possible pancreatitis, nivolumab should be discontinued and consultation with a gastroenterologist should be considered.

6.1.9 Uveitis and Visual Complaints

Immune therapies have been uncommonly associated with visual complaints. Inflammation of components within the eye (eg, uveitis) is an uncommon but clinically important event. An ophthalmologist should evaluate visual complaints. Topical corticosteroids may be used to manage low grade events. Low-grade events that do not resolve and high-grade events should be managed with systemic corticosteroids.

6.1.10 Nivolumab administration should be delayed for the following:

- Any Grade ≥ 2 non-skin, drug-related AE, with the following exceptions:
 - Grade 2 drug-related fatigue or laboratory abnormalities do not require a treatment delay
- Any Grade 3 skin, drug-related AE
- Any Grade 3 drug-related laboratory abnormality, with the following exceptions for lymphopenia, leukopenia, AST, ALT, total bilirubin, or asymptomatic amylase or lipase:
 - Grade 3 lymphopenia or leukopenia does not require dose delay
 - If a subject has a baseline AST, ALT, or total bilirubin that is within normal limits, delay dosing for drug-related Grade ≥ 2 toxicity
 - If a subject has baseline AST, ALT, or total bilirubin within the Grade 1 toxicity range, delay dosing for drug-related Grade ≥ 3 toxicity
 - Asymptomatic amylase or lipase does not require dose delay

- Any AE, laboratory abnormality, or intercurrent illness which, in the judgment of the investigator, warrants delaying the dose of study medication

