6.1.11 Criteria to Resume Treatment

Patients may resume treatment with study drug when the drug-related AE(s) resolve to Grade ≤1 or baseline value, with the following exceptions:

- Patients may resume treatment in the presence of Grade 2 fatigue
- Patients who have not experienced a Grade 3 drug-related skin AE may resume treatment in the presence of Grade 2 skin toxicity
- Patients with baseline Grade 1 AST/ALT or total bilirubin who require dose delays for reasons other than a 2-grade shift in AST/ALT or total bilirubin may resume treatment in the presence of Grade 2 AST/ALT OR total bilirubin
- Patients with combined Grade 2 AST/ALT AND total bilirubin values meeting discontinuation parameters (Discontinuation Section, Section 12.0) should have treatment permanently discontinued
- Drug-related pulmonary toxicity, diarrhea, or colitis, must have resolved to baseline before treatment is resumed
- Drug-related endocrinopathies adequately controlled with only physiologic hormone replacement may resume treatment

If the criteria to resume treatment are met, the subject should restart treatment at the next scheduled timepoint per protocol. However, if the treatment is delayed past the next scheduled timepoint per protocol, the next scheduled timepoint will be delayed until dosing resumes.

If treatment is delayed > 6 weeks, the subject must be permanently discontinued from study therapy, except as specified in discontinuation section.

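### If a drug-related creatinine rise is classed as a laboratory abnormality, section 6.1.10 permits nivolumab dosing at Grade 2 where the renal table in 6.1.6 says to hold, and section 12.0 omits the renal table's 7-day stop

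*Combined protocol and SAP*

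**What the plan says.** **Renal table (6.1.6).** Grades are defined only by creatinine. The row that opens "Grade 2-3 (Creatinine > 1.5x baseline to" runs to 6 x ULN and covers Grades 2 and 3 together. Its action is to delay nivolumab and give methylprednisolone 0.5-1 mg/kg/day or equivalent. Its follow-up column has a branch, "If elevations persist >7 days or worsen", that moves the patient to Grade 4 management, where nivolumab is discontinued. The section also reports: "Most cases were Grade 2 or Grade 3 and based on creatinine elevation".

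**General delay rule (6.1.10).** Drug-related non-skin events of Grade 2 or higher require a delay, with this exception: "Grade 2 drug-related fatigue or laboratory abnormalities do not require a treatment delay". Grade 3 laboratory abnormalities do require a delay, apart from named exceptions that do not include creatinine. The stricter Grade 2 handling is for liver tests: "If a subject has a baseline AST, ALT, or total bilirubin that is within normal limits, delay dosing for drug-related Grade" 2 or higher. Pancreatic enzymes are also named: "Asymptomatic amylase or lipase does not require dose delay". A final item covers discretion: "Any AE, laboratory abnormality, or intercurrent illness which, in the judgment of the investigator, warrants delaying the dose of study medication".

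**Resumption (6.1.11).** "Patients may resume treatment with study drug when the drug-related AE(s) resolve to Grade" 1 or lower, or to the baseline value. Creatinine has no exception. A delay beyond 6 weeks ends treatment, except as section 12.0 allows.

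**Discontinuation (12.0).** Grade 3 non-skin events lasting more than 7 days end nivolumab, but laboratory abnormalities are taken out of that rule. Grade 3 laboratory abnormalities need not lead to discontinuation, apart from thrombocytopenia (beyond 7 days or with bleeding) and listed liver-test values. Creatinine is not listed.

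**The concern.** The instruction for the same patient depends on a classification that the protocol does not make. A creatinine rise can be called a renal adverse event or a laboratory abnormality. The second label is natural, because 6.1.6 grades the event by a blood result and says most past cases rested on that result.

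Nivolumab dose reductions are not permitted (6.1), so delay and discontinuation are the main dosing controls, and these are the instructions that diverge. Section 9.0 schedules chemistry, including creatinine, at infusion visits, so the choice between holding and dosing arises there. A clinician working from 6.1.10 could infuse a patient with suspected immune-mediated nephritis whom 6.1.6 would hold and treat with steroids.

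**Working it through.** The plan states no figure on this point. The check sets the sections side by side, grade by grade, and then looks for a rule that ranks them.

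**Step 1. Creatinine rise read as a laboratory abnormality.**

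| Situation | Renal table (6.1.6) | General rules | Result |
|---|---|---|---|
| Grade 2 | Delay, steroids | 6.1.10: delay not required | General rule more permissive |
| Grade 3, first 7 days | Delay, steroids | 6.1.10: delay required | Agree on the hold |
| Grade 3, beyond 7 days | Grade 4 management: discontinue | 12.0: discontinuation not required; 6.1.10 and 6.1.11: hold until Grade 1 or lower, or baseline | Permanent stop versus hold and possible resumption |
| Grade 4 | Discontinue | 12.0: discontinue | Agree |

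In the third row, the 6-week limit narrows the difference. It does not close it, because 12.0 exempts interruptions for prolonged steroid tapers and 6.1.6 asks for a taper of at least 1 month.

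For a Grade 2 rise lasting beyond 7 days, 6.1.6 also moves to Grade 4 management. Section 12.0 has no matching rule, so it is silent there rather than contrary.

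**Step 2. The same rise read as a clinical renal adverse event.** Section 6.1.10 delays at Grade 2 or higher, 12.0 stops a Grade 3 event beyond 7 days, and 6.1.11 governs resumption. Both differences in Step 1 disappear. Only the silence on prolonged Grade 2 remains.

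**Step 3. An example.** Section 3.1 admits patients with creatinine up to 1.5 x ULN. Take a baseline of 1.0 x ULN rising to 1.6 x ULN:

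- ratio to baseline = 1.6 / 1.0 = 1.6, above the 1.5 lower edge of the Grade 2-3 row and well below 6 x ULN;
- for a patient at the eligibility limit, that lower edge is 1.5 x 1.5 = 2.25 x ULN.

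Calling the 1.6 x ULN value Grade 2 is an assumption, because 6.1.6 gives no cut between Grades 2 and 3. On it, 6.1.6 holds the infusion and starts steroids, while 6.1.10 on the laboratory reading does not require the hold.

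**Step 4. Is there a tie-breaker?**

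- The discordance clause in 11.1.2 covers only the recording and reporting of adverse events.
- Section 6.0 says Grade 3-4 immune-related toxicity generally ends nivolumab. It is silent on Grade 2 and ranks no section.
- The investigator-judgment items in 6.1.10 and 12.0 allow stricter action but do not say which section governs.
- The move to Grade 4 management in 6.1.6 directs treatment. It does not regrade the event for the purposes of 12.0.

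No text settles the order.

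**The case against.** The strongest reply is that nothing here is contradictory. The general rules say only that a delay or stop is not required, so a clinician who follows 6.1.6 complies with every section. The section is headed as renal adverse events, and section 2.4.2.4 lists renal events as a Select AE category, which favours the clinical reading. This stands as a limit: the defect is an ambiguity, not an order to dose. It does not remove the point, because 6.1.10 and 12.0 are the operative lists for delay and discontinuation, and 12.0 itself treats other numeric blood results (platelets, liver tests) as laboratory abnormalities.

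Three stronger readings are tempting and should not be drawn.

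- *That the general rules allow infusion during a persistent Grade 3 rise.* They do not. Section 6.1.10 requires the hold and 6.1.11 bars resumption until recovery. Only the permanent stop is in dispute.
- *That creatinine is the only organ rule out of line.* It is not. Section 6.1.3 delays for Grade 2 liver tests whatever the baseline, while 6.1.10 waits for Grade 3 when the baseline is Grade 1. That mismatch is at least an explicit allowance; the one for creatinine comes from omission.
- *That a patient count can be read from the background data.* Table 2.4.2.4-1 is titled as events in at least 10 of 306 patients and has no renal row, which might suggest at most 9 / 306 = 2.9%. But the table prints a hypersensitivity row with 4 patients, so a missing row is a poor guide. The data are also from solid-tumour monotherapy, and 6.1.6 says creatinine abnormalities are common in CLL.

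**Conclusion.** The point holds, on the condition that the rise is classed as a laboratory abnormality. The substantive conflict is at Grade 2: hold with steroids against dosing permitted. At Grade 3 it shrinks to a permanent stop after 7 days against a hold with possible resumption, subject to the 6-week limit and its exceptions. Investigator judgment can close either gap in practice, but no stated rule does.

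The number of patients affected cannot be estimated from the documents. It is likely small, in a study of at most 72 patients with all nivolumab given at one centre. The response endpoints, the two-stage design and the definition of a toxicity-monitoring event do not change. This is a dosing-safety ambiguity that should be corrected because the correction is nearly free; it does not threaten the trial's conclusions.

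**What to change.** Make two targeted edits.

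1. In 6.1.10, add creatinine to the named laboratory items: a drug-related creatinine elevation of Grade 2 or higher requires delay, as in 6.1.6.
2. In 12.0, add to the laboratory abnormalities that require discontinuation: creatinine elevation persisting more than 7 days or worsening, as in 6.1.6. This also covers prolonged Grade 2, where 12.0 is now silent.

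Do not add a general sentence giving the organ-specific sections precedence. It would override the explicit allowance in 6.1.10 for patients with Grade 1 baseline liver tests and force Grade 2 liver delays there.

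The cost is a line or two in an amendment, with no new tests or data. The downside is a few more nivolumab delays or discontinuations.

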6.1.11 Criteria to Resume Treatment

Patients may resume treatment with study drug when the drug-related AE(s) resolve to Grade ≤1 or baseline value, with the following exceptions:

- Patients may resume treatment in the presence of Grade 2 fatigue
- Patients who have not experienced a Grade 3 drug-related skin AE may resume treatment in the presence of Grade 2 skin toxicity
- Patients with baseline Grade 1 AST/ALT or total bilirubin who require dose delays for reasons other than a 2-grade shift in AST/ALT or total bilirubin may resume treatment in the presence of Grade 2 AST/ALT OR total bilirubin
- Patients with combined Grade 2 AST/ALT AND total bilirubin values meeting discontinuation parameters (Discontinuation Section, Section 12.0) should have treatment permanently discontinued
- Drug-related pulmonary toxicity, diarrhea, or colitis, must have resolved to baseline before treatment is resumed
- Drug-related endocrinopathies adequately controlled with only physiologic hormone replacement may resume treatment

If the criteria to resume treatment are met, the subject should restart treatment at the next scheduled timepoint per protocol. However, if the treatment is delayed past the next scheduled timepoint per protocol, the next scheduled timepoint will be delayed until dosing resumes.

If treatment is delayed > 6 weeks, the subject must be permanently discontinued from study therapy, except as specified in discontinuation section.

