2.5.2 Ibrutinib forms a specific bond with the cysteine-481 of BTK.⁴⁶ It leads to highly potent BTK inhibition with an IC₅₀ of 0.5nM.⁴⁷ Treatment of CLL cells with ibrutinib induced apoptosis in a dose- and time- dependent manner which was independent of baseline cytogenetics, *IGHV* mutational status or baseline BTK protein expression.⁴⁸ Ibrutinib also induced apoptosis in normal B cells, but this was significantly less than that seen in CLL cells, indicating that CLL cells are more sensitive to ibrutinib than normal B cells. Ibrutinib treatment of CLL cells inhibited downstream signaling pathways including ERK1/2 phosphorylation, CD40L induced AKT phosphorylation and CD40L induced NF- κ B DNA binding.⁴⁸ Ponader et al. evaluated the role of the tissue microenvironment of CLL cells and its effect on treatment with ibrutinib.⁴⁹ They reported that ibrutinib treatment significantly inhibited CLL cell migration and survival in a nurse-like cells (NLC) co-culture assay. In this model, ibrutinib treatment significantly decreased the levels of CCL3 and CCL4 and inhibited chemotaxis towards CXCL12 and CXCL13. In an adoptive transfer TCL1 mouse model, ibrutinib treatment delayed CLL progression.⁴⁹ Ibrutinib has impressive monotherapy activity in patients with relapsed CLL. Byrd et al. reported an ORR of 71% with ibrutinib in the relapsed setting.^{50,51} However, most of the responses with ibrutinib are partial responses. The 30-month PFS was reported as 68.4%, with median PFS of 28.1 months in patients with del(17p) (O'Brien et al. ASCO 2014). Ibrutinib is approved by the FDA for patients with CLL who received at least one prior therapy and in patients with del(17p). Ibrutinib is well tolerated with diarrhea being the most common adverse event (mostly grade 1-2).⁵²

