6.1.2 Gastrointestinal adverse events

Gastrointestinal AEs have been observed following treatment with nivolumab. Most cases of diarrhea were low grade (Grade 1-2). Colitis occurs less frequently than diarrhea. High grade cases of diarrhea and colitis were managed with corticosteroids and in all cases the events resolved. Early recognition and treatment of diarrhea and colitis are critical to its management. Patients should be advised to seek medical evaluation if they develop new onset diarrhea, blood in stool, or severe abdominal pain, or if they have worsening of baseline diarrhea. As GI symptoms are common in patients with CLL, it is important that an evaluation/work-up distinguish between non-drug-related causes (eg, infection, progression of disease) and a possible drug-related AE as the management is quite different. Rule out non-inflammatory causes. If non-inflammatory cause is identified, treat accordingly and continue nivolumab therapy. Opiates/narcotics may mask symptoms of perforation.

NOTE: As diarrhea could occur from the use of ibrutinib, patients with grade 2 diarrhea should have their ibrutinib held as well.

Grade of Diarrhea/Colitis	Management	Follow-up
Grade 1 Diarrhea (Increase of <4 stools per day over baseline) Colitis (Asymptomatic)	
 Continue nivolumab Symptomatic treatment 	
 Close monitoring for worsening symptoms If worsens: 
 Treat as Grade 2 or 3-4
Grade 2 Diarrhea (Increase of 4 - 6 stools per day over baseline) Colitis (Abdominal pain; blood in stool)	
 Delay nivolumab Symptomatic treatment 	If improves to grade 1: 
 Resume nivolumab If persists > 5-7 days or recur: 
 Steroids: 0.5-1.0 mg/kg/day methylprednisolone or oral equivalent When symptoms improve to grade 1, taper steroids over

		
at least 1 month, consider prophylactic antibiotics for opportunistic infections, and resume nivolumab
 
If worsens or persists > 3-5 days with oral steroids:
 
 ▪ Treat as Grade 3/4

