 - ii. All serious adverse events regardless of attribution to the study drug(s).
 - iii. Any grade adverse event regardless of attribution to the study drug(s) that results in any dose modification.
- d. Hematologic adverse events will not be recorded or reported for studies in patients with acute leukemia, myelodysplastic syndrome, chronic lymphocytic leukemia, or chronic myeloid leukemia in blast phase except for:
 - i. Prolonged myelosuppression as defined by the NCI-CTCAE criteria specific for leukemia, e.g. marrow hypocellularity on day 42 or later (6 weeks) from start of therapy without evidence of leukemia (< 5% blasts), or that results in dose modifications, interruptions or meets the protocol definition of DLT or SAE.
 - e. Serious adverse events will be reported according to institutional policy.
 - f. Protocol specific language regarding the recording and reporting of adverse and serious adverse events will be followed in the event of discordance between the protocol and Leukemia-specific adverse event recording and reporting guidelines.

11.1.3 Abnormal hematologic values will not be recorded on the case report form. For abnormal chemical values, the apogee or nadir (whichever is appropriate) will be reported per course on the case report form.

11.1.4 All events that are not listed as expected in section 11.1.2 will be collected for the purpose of grading, and determining attribution to study drugs by the PI using the following scale:

Unrelated: The AE is clearly NOT related to the intervention.

Unlikely: The AE is doubtfully related to the intervention.

Possible: The AE may be related to the intervention.

Probable: The AE is likely related to the intervention.

Definite: The AE is clearly related to the intervention.

11.1.5 All grade 3 and greater non-hematological events that are felt to be related to protocol treatment drugs will be documented on the toxicity log and entered into the case report form. The toxicity log and case report form data must reflect relationship to the drug the event is felt to be related to.

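### After grade 2 diarrhea or colitis, the 6.1.2 table resumes nivolumab at grade 1, but 6.1.11 forbids this until the event is back to baseline

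*Combined protocol and SAP*

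**What the plan says.** Section 6.1.11 opens with a general rule: "Patients may resume treatment with study drug when the drug-related AE(s) resolve to Grade ≤1 or baseline value, with the following exceptions". One of the listed exceptions is: "Drug-related pulmonary toxicity, diarrhea, or colitis, must have resolved to baseline before treatment is resumed".

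The grade 2 row of the diarrhea/colitis table in 6.1.2 delays nivolumab and then gives two ways back:

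- **Without steroids.** Under the condition "If improves to grade 1" the instruction is to resume nivolumab.
- **With steroids**, if the event persists beyond 5-7 days or recurs. The table says "When symptoms improve to grade 1, taper steroids over" and continues "at least 1 month, consider prophylactic antibiotics for opportunistic infections, and resume nivolumab".

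The same table defines grade 1 diarrhea as "Increase of <4 stools per day over baseline" and grade 1 colitis as asymptomatic.

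Three other places matter. The last bullet of 6.1.10 lets the investigator delay a dose for any adverse event that in his or her judgment warrants it. The grade 2 row of 6.1.1 starts the steroid taper for pneumonitis when symptoms are close to baseline, and then resumes nivolumab. The discordance clause, 11.1.2 f, reads "Protocol specific language regarding the recording and reporting of adverse and serious adverse events will be followed in the event of discordance".

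**The concern.** Two sections under the same nivolumab heading set different thresholds for the same restart decision. A physician managing diarrhea is likely to turn to the table for that event and grade, and that table gives the looser instruction. If it is followed, a patient with residual bowel symptoms is given a checkpoint inhibitor again when another section says this must not happen. The situation is plausible in this trial: the protocol notes that either drug can cause diarrhea, and its background section calls diarrhea the most common adverse event of ibrutinib. The choice of threshold also sets how long nivolumab is withheld, which feeds into the rule that stops it after a delay of more than 6 weeks.

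**Working it through.** The plan states no figure on this point, so the check is a comparison of the text.

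1. **Same drug?** Yes. Both 6.1.2 and 6.1.11 sit under 6.1, dose modification for nivolumab.
2. **Same patients?** Yes. 6.1.2 asks that non-inflammatory causes be ruled out and continues nivolumab where one is found, so its delay rows concern drug-related events. The 6.1.11 exception is also limited to drug-related events.
3. **Is grade 1 the same state as baseline?** No. Grade 1 diarrhea is fewer than 4 stools a day above baseline, so in whole stools 1, 2 or 3 extra; baseline is 0 extra. For colitis the gap is asymptomatic disease against baseline. The structure of 6.1.11 agrees: its general rule already accepts grade 1, so an exception in which baseline meant grade 1 would be empty.
4. **A patient who was at grade 2 and is now at grade 1:**
   - 6.1.2, no steroids: resume now.
   - 6.1.2, steroids: start the taper at grade 1, continue it for at least a month, then resume. The patient may have reached baseline by then, but the table does not ask for this.
   - 6.1.11: do not resume until baseline.
   - 6.1.10: further delay is allowed on investigator judgment.

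   Redosing at grade 1 therefore breaks 6.1.11. Waiting satisfies 6.1.11 and is covered by 6.1.10.
5. **Does any clause settle it?** No. The hold rule in 6.0 concerns grade 3 or 4 toxicity, 12.0 gives criteria for stopping, and 11.1.2 f is confined to adverse event recording and reporting. Neither 6.1.2 nor 6.1.11 refers to the other on this point.
6. **Is the mismatch confined to 6.1.2?** No. The same 6.1.11 bullet covers pulmonary toxicity, and the grade 2 row of 6.1.1 resumes nivolumab after a taper begun near baseline, without requiring full return to it.

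**How many patients?** The only usable data are treatment-related diarrhea counts from nivolumab monotherapy in solid tumors (Tables 2.4.2.3-1 and 2.4.2.4-1). Assuming patients are counted by worst grade:

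- All doses: 41 any grade − 3 grade 3-4 = 38 grade 1-2; 38/306 = 12.4%.
- At 3 mg/kg, the study dose: 6 − 0 = 6; 6/54 = 11.1%.

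These give context and are not limits. They combine grade 1 with grade 2, although only grade 2 events that linger at grade 1 count, so they could be too high. They omit other gastrointestinal events (any such event: 43 patients against 41 with diarrhea) and all diarrhea due to ibrutinib, so they could also be too low.

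**The case against.** The best defense is that a careful reader can tell which rule is meant. Section 6.1.11 is the dedicated section on resuming treatment, comes after the organ tables, names diarrhea and colitis, uses mandatory language, and adds that dosing restarts at the next scheduled timepoint once its criteria are met. All nivolumab is given at one center, and Appendix 3 reserves protocol-specific decisions to that center's physicians, which limits inconsistent application. This stands as evidence of intent, and the stricter reading is probably what was meant. But it is an inference, and the table still directs earlier redosing.

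Three stronger readings are tempting, and the documents do not support them:

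- A reader might infer that the physician breaches a rule whichever section is followed. That is not so, because 6.1.10 permits waiting.
- A reader might infer that 6.2 returns ibrutinib at grade 1 while nivolumab must still wait. The restart threshold in 6.2 follows interruptions for grade 3 or greater non-hematological toxicity, or for severe hematological toxicity. The grade 2 diarrhea hold is a separate note with no restart threshold.
- A reader might scale 38/306 to the 72 planned patients and call the result a ceiling. It is not one, for the reasons given with the counts. In addition, each cohort can stop after its first 9 patients.

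**Conclusion.** The inconsistency is real and is in the current text. For drug-related grade 2 diarrhea or colitis, the 6.1.2 table directs nivolumab re-exposure at a point where 6.1.11 prohibits it. The gap is up to 3 stools a day over baseline, or asymptomatic colitis. The error has one direction, toward redosing too early, because a compliant and safer course is always open. Grade 2 pneumonitis in 6.1.1 has a similar but smaller mismatch.

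The number of patients affected cannot be bounded from the documents: the monotherapy counts do not split grades 1 and 2, and no rate is given for the combination. Neither the Simon two-stage design nor the toxicity stopping boundaries change. This is a patient-safety and dosing-consistency point that should be corrected at the next amendment. The conclusion rests only on the protocol's own grade definitions and on reading the 6.1.2 delay rows as applying to drug-related events.

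**What to change.** Two wording changes:

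1. In the grade 2 row of 6.1.2, change both resume instructions, with and without steroids, to: *resume nivolumab when resolved to baseline (see 6.1.11)*.
2. Add one sentence to 6.1 saying that the 6.1.11 resume criteria govern where an organ table differs. This also covers grade 2 pneumonitis in 6.1.1. It should be limited to tables that are looser than 6.1.11. The grade 2 neurologic row (6.1.7) and the no-steroid path of the grade 2 hepatic row (6.1.3) already ask for baseline where the general rule accepts grade 1, and an unqualified sentence could relax them.

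No patients, visits or data are added. The cost is that some nivolumab delays become longer. A few patients whose grade 1 diarrhea persists without a steroid taper could reach the 6-week discontinuation rule. That group should be small, because grade 2 diarrhea that persists beyond 5-7 days or recurs goes to steroids, and 12.0 exempts prolonged tapers from the limit. The amendment should confirm that stopping nivolumab in the remaining cases is intended.
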